3.5 Sample Size

Sample size

Based on pre-randomization data collected from January to December 2017, we estimate 5360 patients will be enrolled across 20 study sites over the 18-month enrolment period. Other study intervals ranging from 12 to 24 months are considered.

Justification

Original detectable effect size estimates: The study is based on the health center being the unit of randomization and aims to demonstrate the superiority of the intervention arm. The sample size calculation uses formulae appropriate for cluster-randomized trials with a parallel design and stratified and/or restricted randomization, including the addition of one extra cluster per arm to allow for the loss of degrees of freedom due to stratification to obtain conservative estimates.⁷ The original detectable effect size estimates were based on the outcome being the proportion of patients treated for microbiologically-confirmed TB within two weeks of referral for sputum-based testing. A type I error of 5% and power of 90% was assumed. Pre-randomization data collected from January to December 2017 from the 20 selected trial sites in Uganda suggested that the average proportion of patients referred for TB evaluation who initiate treatment for active TB within two weeks would be 6.7%, and the coefficient of variation (k) between clusters is 0.36, with a harmonic mean of 268 patients enrolled at each health center cluster during the 18-month enrolment period. Based on these assumptions and assuming a type I error of 5%, we will have 90% power to detect a 6% or greater absolute increase in the outcome proportion in the intervention arm (see **Table 1**). Table 1 also shows detectable absolute effect sizes with varying power (80%, 85%, 90%) during various trial time intervals and respective average cluster size estimates.

[figure not shown]
The minimum detectable effect size is based on published literature, our preliminary data demonstrating the increased sensitivity of Xpert Ultra vs. smear microscopy (95% vs. 40%), and reduced pre-treatment loss to follow-up expected in the intervention vs. control arms due to rapid, onsite molecular testing (7% vs. 30%). When applying these parameters to a population of 1000 individuals with TB prevalence of 10%, we would expect 95 patients to be diagnosed with TB and 88 to start treatment within 14 days in the intervention arm, and 40 patients to be diagnosed with TB and 28 to start treatment within 14 days in the control arm. Thus, the expected difference in the primary outcome proportion would be 8.8% vs. 2.8%, or 6%.⁸

Table 1. Absolute difference in the proportion of clinic attendees initiating TB treatment within 14 days of initial sputum submission, among those referred for TB testing

Average cluster size	Effect size (10 clusters per arm, $k=0.36$)		
	80% Power	85% Power	90% Power

178 (12 months)	5.9%	6.5%	7.4%
223 (15 months)	5.7%	6.3%	7.1%
268 (18 months)	5.5%	6.1%	6.9%
312 (21 months)	5.4%	6.0%	6.7%
357 (24 months)	5.3%	5.9%	6.6%

Figure 1. Effect size by cluster size. Number of clusters per arm is 10, $k=0.36$.

The primary outcome was changed to a count of the number of adults diagnosed and treated with TB at the cluster-level. The new primary outcome better reflects the intended effect of the multi-component intervention to drive more people who present to health facilities through the entire TB diagnostic evaluation cascade of care, including being screened for TB, tested for TB (if screen-positive), diagnosed with TB (if tested) and initiated on treatment (if diagnosed). Process re-design is expected to help improve the number screened and tested. Onsite molecular testing is expected to increase the numbers diagnosed (increased sensitivity) and treated (faster turn-around time and reduced workload). Performance feedback is expected to maintain improvement along each step of the cascade. Thus, the intervention is expected to increase both the number of patients entering and completing the cascade of care.

Revised detectable effect size estimates: The revised detectable effect size estimates are for the outcome being the number of patients treated for microbiologically-confirmed TB within two weeks of referral for sputum-based testing. We first used 10 months of pre-intervention period data across all 20 clinics to assess 1) the geometric mean number of patients diagnosed and treated for TB within 14 days (new primary outcome), the natural log (ln) of the geometric mean and 3) the standard deviation of the natural log at control sites, intervention sites and overall. For the pre-intervention period, the intervention clinics have a lower geometric mean number of clinic attendees who were diagnosed with TB and started on TB treatment within 14 days compared with the control arm (table 2).

Table 2: summary data from the baseline period

	Geometric mean	Mean of ln outcome	SD of ln outcome
Control	14.70	2.69	0.23

Intervention	6.49	1.87	0.32
--------------	------	------	------

We then estimated the detectable effect size (expressed as a geometric mean ratio). The calculations assume the same parameters as for the original primary outcome (10 clinics/arm, 18-month trial duration to achieve geometric mean of 268 patients/cluster in control and intervention arms). Table 3 below shows the detectable effect size assuming within-arm SD of ln outcome of 0.2 to 0.3 and power of 80-90%. The detectable effect sizes shown below are conservative (calculations do not take into account the baseline differences between arms in the new primary outcome and are based on 10-months rather than full 24-months of pre-intervention data). Final calculations will be repeated once baseline data is fully entered and available for analysis.

Table 3: Detectable effect sizes

SD of ln outcome	Geometric Mean Ratio of the new primary outcome (intervention vs control)	
	80% power	90% power
0.2	1.30	1.36
0.3	1.49	1.58

We believe a GMR of 1.30-1.58 is a reasonable detectable effect size. Xpert MTB/RIF is twice as sensitive as smear microscopy (double the number of confirmed TB cases) and we expect onsite testing to reduce pre-treatment loss to follow-up by at least half (from 30% to <15%).

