for cluster-randomized trials with a parallel design and stratified and/or restricted randomization, including the addition of one extra cluster per arm to allow for the loss of degrees of freedom due to stratification to obtain conservative estimates.²⁶ The outcome is the proportion of patients treated for microbiologically-confirmed TB within two weeks of referral for sputum-based testing. A type I error of 5% and power of 90% is assumed. Pre-randomization data collected from February to July 2017 from the 20 selected trial sites in Uganda suggests the average proportion of patients referred for TB evaluation who initiate treatment for active TB within two weeks is 8.6%, and the coefficient of variation (k) between clusters is 0.27, with a harmonic mean of 325 patients enrolled at each health center cluster during the 18-month enrolment period. Based on these assumptions and assuming a type I error of 5%, we will have 90% power to detect a 6% or greater absolute increase in the outcome proportion in the intervention arm with a trial duration of 18 months (see **Table**). Table 1 also shows detectable absolute effect sizes with varying power (80%, 85%, 90%) during various trial time intervals and respective average cluster size estimates.

Average cluster size	Effect size (10 clusters per arm, $k=0.27$)		
	80% Power	85% Power	90% Power
215 (12 months)	5.3%	5.8%	6.4%
270 (15 months)	5.1%	5.5%	6.2%
325 (18 months)	4.9%	5.4%	6.0%
375 (21 months)	4.8%	5.3%	5.8%
430 (24 months)	4.7%	5.2%	5.7%

Aim 2

The sample size for Aim 2 analyses is either fixed (process metrics; provider surveys and focus groups) by parameters of the clinical trial or based on feasibility considerations (patient surveys and provider in depth interviews). For quantitative analyses, the sample size is sufficiently large (data on 3400 patients for process metrics analyses, 800 patient surveys, and 100-200 provider surveys) to enable multivariable analysis to identify factors associated with intervention adoption and maintenance.

Aim 3

As Aim 3 is primarily a modeling aim, sample size calculations are not applicable. Sample size considerations for the cost data (i.e., number of direct observations through time and motion studies, number of patients completing the cost questionnaires) are based on feasibility considerations and desire to estimate model parameters to sufficient levels of precision, as described above for Aim 2.

Ethical Considerations

Potential risks to participants

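### Section 3.5 claims 90% power for a 6-point increase where its own table gives 6.9 points, and the lower end of the detectable ratio for the count outcome assumes an SD below both observed SDs

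*Combined protocol and SAP*

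**What the plan says.** **Proportion outcome (since replaced).** The amended SAP, section 3.5, takes a control proportion of 6.7% and states that "the coefficient of variation (k) between clusters is 0.36, with a harmonic mean of 268 patients enrolled at each health center cluster". It concludes that "we will have 90% power to detect a 6% or greater absolute increase in the outcome proportion in the intervention arm" and refers to Table 1. At 268 per clinic (18 months), Table 1 lists 5.5, 6.1 and 6.9 percentage points for 80%, 85% and 90% power. The same sentence and figures stand in SAP version 1.0, section 3.5, and in the current protocol under Sample Size Considerations, Aim 1.

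The earlier protocol version used a proportion of 8.6% and reported that "the coefficient of variation (k) between clusters is 0.27, with a harmonic mean of 325 patients enrolled at each health center cluster". Its table gives 6.0 points at 90% power.

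**Count outcome (current primary).** Table 2 of the amended SAP gives the SD of the log count from 10 months of baseline data as 0.23 in control clinics and 0.32 in intervention clinics. The text continues: "Table 3 below shows the detectable effect size assuming within-arm SD of ln outcome of 0.2 to 0.3 and power of 80-90" per cent. Table 3 gives 1.30/1.36 at SD 0.2 and 1.49/1.58 at SD 0.3 (80%/90% power). The section ends: "We believe a GMR of 1.30-1.58 is a reasonable detectable effect size".

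**The concern.** The power sentence contradicts the table it points to, and the conflict is visible without any formula: Table 1 reaches 6.1 points only at 85% power, and its 90% column never falls below 6.6, even at 24 months.

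For the count outcome, one of the two SDs in Table 3 is smaller than either SD printed just above it, and the text gives no basis for it. That row supplies the 1.30 in the endorsed range. A reader who takes 1.30 as detectable with 80% power credits the trial with more ability to find a modest effect (roughly 1.3 to 1.45) than the baseline data support.

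**Working it through.** **1. Proportion outcome**

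Inputs from section 3.5: p0 = 0.067, k = 0.36, m = 268, 10 clinics per arm, type I error 5%, and one extra cluster per arm for stratification. Two assumptions are mine: a two-sided test (the plan reports 95% intervals) and the usual additional cluster in the standard formula. Together the allowances leave c = 10 − 2 = 8.

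Formula: c = (z_0.975 + z_power)² × V / (p1 − p0)², where V = p0(1 − p0)/m + p1(1 − p1)/m + k²(p0² + p1²).

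*Reproducing Table 1.* Solving for p1 − p0 at m = 268 gives 5.58, 6.15 and 6.94 points, against the printed 5.5, 6.1 and 6.9. All 15 cells of Table 1 agree within 0.1 point.

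*Power for 6 points (p1 = 0.127).*
- V = 0.000233 + 0.000414 + 0.002672 = 0.003319
- SE = sqrt(0.003319/8) = 0.02037
- 0.06/0.02037 − 1.96 = 0.986, so power is **83.8%**

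*Other conventions at m = 268:*

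| Convention | Detectable at 90% | Power for 6 points |
|---|---|---|
| Two-sided, c = 8 | 6.94 | 83.8% |
| Two-sided, c = 9 | 6.34 | 87.8% |
| Two-sided, c = 10 | 5.86 | 90.9% |
| One-sided, c = 8 | 5.94 | 90.3% |

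The last two reach 90%, but one drops the stated allowance and the other is one-sided. Only the first row reproduces Table 1.

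*Source of the 6 points.* The earlier protocol inputs (8.6%, k = 0.27, m = 325) give 5.97 points at 90% power by the same formula, matching that version's 6.0. The inputs and table were updated; the sentence was not.

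**2. Count outcome**

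*Reproducing Table 3.* A two-sided 5% t-test on log counts, 10 clinics per arm and 18 df, gives 1.303/1.359 at SD 0.2 and 1.488/1.584 at SD 0.3. Table 3 is correct.

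*With the printed SDs.* Pooled SD = sqrt((0.23² + 0.32²)/2) = 0.279.

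| SD of log count | Detectable ratio, 80%/90% | Power at 1.30 | Power at 1.58 |
|---|---|---|---|
| 0.23 (control) | 1.36/1.42 | 67% | 99% |
| 0.28 (pooled) | 1.45/1.53 | 51% | 93% |
| 0.32 (intervention) | 1.53/1.63 | 41% | 86% |

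*Could 18-month counts bring the SD to 0.2?* Poisson noise in a log count is about 1/sqrt(events). It depends on the events assumed per clinic:
- 268 × 0.067 = 18 events: 0.24. With the intervention arm at 1.30 times that (23.3), pooled over arms: 0.22.
- Each arm scaled from its own 10-month mean, intervention raised by 1.30 (14.70 × 1.8 = 26.5; 6.49 × 1.8 × 1.30 = 15.2): 0.23.
- Both arms starting at the control mean (26.5 and 34.4): 0.18.

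At 0.18 the room left for true between-clinic variation is about sqrt(0.2² − 0.183²) = 0.08. In the other cases there is none.

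*At the protocol's enrolment.* 11,283/20 = 564 per clinic. If 6.7% still held, that is 37.8 events, pooled noise of 0.153, and sqrt(0.2² − 0.153²) = 0.13 left over.

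**The case against.** **The sentence sits under the heading for the original estimates, the outcome has been replaced, and Table 1 beside it is right.** This stands as a limit: the error has no bearing on power for the count outcome. It is still current text in the protocol and SAP, built on the updated inputs.

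**The SAP expected 6 points, so a reader might infer that the trial was underpowered for its own target.** The documents do not support that. Section 3.5 writes "Thus, the expected difference in the primary outcome proportion would be 8.8% vs. 2.8%, or 6" per cent. The 84% applies to 6.7% versus 12.7%. The same formula with k = 0.36 and m = 268 gives about 99% for 2.8% versus 8.8%, because the variance falls with the proportions.

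**Table 3 is a grid around the pooled SD, shows each ratio beside its SD, and 18-month counts are less noisy than 10-month counts.** In part this stands. The grid does bracket 0.28, and Poisson noise is not firmly above 0.2. But 0.2 needs almost no between-clinic variation, and the closing sentence endorses the range without that condition.

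**A reader might also infer that Table 2 prints standard errors.** The printed SDs are below the Poisson noise of their own means (1/sqrt(14.70) = 0.26; 1/sqrt(6.49) = 0.39), and they imply a baseline gap between arms of 0.82/sqrt((0.23² + 0.32²)/10) = 6.6 standard errors. That justifies a query, but nothing in the documents settles it. The text says it assessed "the standard deviation of the natural log at control sites, intervention sites and overall", yet the overall value is not printed.

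**Nor is the word conservative shown to be wrong.** The SAP says "The detectable effect sizes shown below are conservative (calculations do not take into account the baseline differences between arms in the new primary outcome". The primary model in section 4.4.3 adjusts for the baseline count, which in Table 2 differs by arm. Whether that gains or loses precision depends on a within-arm correlation that the documents do not give.

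**Conclusion.** Two statements need correcting.

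1. The power sentence is wrong as written. On the stated inputs the design has 90% power for 6.9 points, or about 84% for 6.7% versus 12.7%. This rests on a two-sided test and the two-cluster allowance, which is the convention that reproduces Table 1.
2. The lower end of the 1.30 to 1.58 range is not supported by the plan's baseline data. At the pooled printed SD the detectable ratio is 1.45/1.53 and power at 1.30 is 51%, against the 80% implied by the 0.2 row. The upper end is reasonable: 1.58 has 93% power at SD 0.28 and 86% at 0.32. This takes the printed values as SDs and as a guide to the 18-month SDs.

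It would be wrong to conclude that the trial cannot detect the effect it hopes for. Doubling detection and cutting pre-treatment loss from 30% to 15% implies a ratio of 2 × 0.85/0.70 = 2.43, which has 96% power even at an SD of 0.5. The SD-or-SE question and the conservative wording remain queries.

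**What to change.** - In the protocol and SAP, change the sentence to 90% power for 6.9 points (or about 84% for 6) and label it as applying to the superseded outcome.
- In Table 3, replace the 0.2 row or state what it requires. Add rows at 0.28 (1.45/1.53) and 0.32 (1.53/1.63), and restate the endorsed range to match.
- When the recalculation promised in section 3.5 is done, check the Table 2 SDs against the clinic-level data, print the overall SD, and use one expected enrolment. The SAP has 5360 (20 × 268) and the protocol has 11,283.
- At the same time, either show the net effect of baseline adjustment or limit the word conservative to the ground that can be shown.

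The cost is recalculation, wording and one check of existing data. No patients are added, and the design and analysis do not change. The stated detectable effect becomes slightly less favourable.

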3.2 Study population

Eligibility Criteria

A. Site-level Inclusion Criteria

- a. Use standard (multi-day) sputum smear microscopy as the primary method of TB diagnosis
- b. Participate in NTP-sponsored external quality assurance (EQA) for sputum smear microscopy
- c. Send samples to a district or regional hospital/health center for Xpert testing

B. Site-level Exclusion Criteria

- a. Do not agree to be randomized to standard-of-care vs. intervention arms
- b. Perform sputum smear examination on <150 patients per year (based on 2015 data)
- c. Diagnose <15 smear-positive TB cases per year (based on 2015 data)

C. Patient-level Inclusion Criteria

- a. Initiating TB evaluation at a study health center

D. Patient-level Exclusion Criteria

- a. Have sputum collected for monitoring of response to anti-TB therapy (i.e., recorded as a follow-up patient in routine data source);
- b. Have sputum collected as part of active, community-based case finding (e.g., contact tracing, community outreach campaign) (i.e., noted in the remarks in the NTLP Laboratory Register);
- c. Referred to a study health center for TB treatment after a diagnosis is established elsewhere (i.e., noted in the remarks in the NTLP Laboratory Register)
- d. Started on TB treatment for extra-pulmonary TB only (i.e., recorded as a Disease Class=EP (Extra Pulmonary TB) in the NTLP Treatment Register)

Settings and Locations

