4.1 Sequence Generation

A random allocation sequence will be generated by STATA 14 (StataCorp LP, College Station, TX). Randomisation of clusters to the intervention or control arm was conducted using stratification and restriction. Stratified randomisation was used to help reduce between-cluster variability and achieve balance at baseline. Using data from 2017 on the percentage of adult clinic attendees being investigated for TB who started TB treatment within 14 days, the clusters were stratified into two equal-sized groups – “low” and “high” percentages of this outcome based on the median. Restricted randomisation was used to help ensure balance for key factors. Variables we restricted on were; year cluster enrolled in project (2017 vs. 2018); sputum transport frequency to Xpert hub; distance to Xpert hub; number of patients evaluated for TB; percentage starting TB treatment within 14 days; urban vs. rural health clinics; HIV prevalence; number of facilities per district. For these restriction criteria the overall proportion of unacceptable allocations was calculated and the the validity assessed using the validity matrix.⁹ From a total of 63,504 possible randomisations based on two equal-sized strata, applying the restriction criteria resulted in 11,392 randomisations; one of these was chosen at random.

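### The SAP's baseline table is very hard to reconcile with its randomisation scheme and its k of 0.36, so the SD range of 0.2 to 0.3 behind the detectable ratios is not supported

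*Combined protocol and SAP*

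**What the plan says.** SAP section 3.5 bases the revised detectable effect on baseline counts of the new primary outcome: "We first used 10 months of pre-intervention period data across all 20 clinics". Table 2 prints geometric mean, mean of ln and SD of ln for each arm: "Control 14.70 2.69 0.23" and, for intervention, 6.49, 1.87 and 0.32. The text reads this as a real difference between arms: "the intervention clinics have a lower geometric mean number of clinic attendees who were diagnosed with TB and started on TB treatment". The amended protocol (Sample Size Considerations, Aim 1) and SAP version 1.0 carry the same figures.

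Table 3 then assumes a within-arm SD of ln of 0.2 to 0.3. The SAP calls the results conservative because they ignore the baseline difference and use 10 rather than 24 months of data. It adds: "Final calculations will be repeated once baseline data is fully entered and available for analysis".

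Two other statements bear on the table. For the 2017 proportion treated within 14 days, section 3.5 says that "the coefficient of variation (k) between clusters is 0.36". On allocation, section 4.1 says: "Stratified randomisation was used to help reduce between-cluster variability and achieve balance at baseline". The strata split the clinics at the median of that 2017 percentage. Restriction then covered, among other factors, the number of patients evaluated and "percentage starting TB treatment within 14 days; urban vs. rural health clinics; HIV prevalence".

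**The concern.** The baseline count in a clinic is roughly the number evaluated times the percentage treated within 14 days. Allocation was restricted on both factors and stratified on the second. Arms formed in this way should have similar counts, yet Table 2 shows them 2.27-fold apart and so tightly clustered that they barely overlap. The SDs also leave little room for the between-clinic variation that the same section reports.

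At stake is the stated sensitivity of the trial. Table 3 depends on nothing but the SD and the number of clinics. If the SD is too small, the claim that ratios of 1.30 to 1.58 are detectable is optimistic. If the rows are not the arms, the stated baseline imbalance is not a fact about the arms.

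**Working it through.** **Inputs.** SAP section 3.5: geometric means, means of ln and SDs of ln from Table 2; 10 clinics per arm; one cluster per arm allowed for lost degrees of freedom, leaving 9; 5% type I error (two-sided assumed); 268 patients per clinic in 18 months; 6.7% treated; k = 0.36. SAP section 4.1: 63,504 stratified allocations, of which 11,392 were acceptable.

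**1. Table 3 reproduces.** Detectable ratio = exp[(1.960 + z) × SD × √(2/9)], with z = 0.842 for 80% power and 1.282 for 90%.
- SD 0.2: 1.30 and 1.36.
- SD 0.3: 1.49 and 1.58.

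These are the printed values, so the SD range alone drives the result.

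**2. Table 2 agrees within itself.** ln 14.70 = 2.69 and ln 6.49 = 1.87. The ratio is 14.70/6.49 = 2.27.

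**3. The gap against the printed SDs.** SE = √[(0.23² + 0.32²)/10] = 0.125, and 0.82/0.125 = 6.6 (18 df, p about 4 in a million).

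**4. The SDs against expected variation.**
- Poisson noise in ln is about 1/√mean: 0.26 at 14.7 and 0.39 at 6.49. Both printed SDs are below this.
- k = 0.36 alone gives √ln(1 + 0.36²) = 0.35.
- With the roughly 10 events per clinic expected in 10 months (268 × 10/18 × 0.067), the total is √(1/9.98 + 0.35²) = 0.47.

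**5. Gap and SDs together.**
- I built clinic values matching Table 2 and enumerated all 5 + 5 stratified allocations. About 2, and at most 4, of 63,504 were as extreme. If all 4 had passed restriction, that would be 4/11,392 = 0.04%.
- I also simulated stratified allocation with k = 0.36 and an assumed SD of ln clinic volume from 0 to 0.9, 40,000 runs per setting. The gap and both SDs never occurred together. A gap this large by itself occurred in 0.02% to 9% of unrestricted runs, and in 0.2% to 2% under an assumed 1.5-fold restriction tolerance.

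**6. Table 3 under other SDs.** Expected events in 18 months are 268 × 0.067 = 18.0, so SD = √(1/18.0 + 0.35²) = 0.42. If the printed SDs are standard errors, the SDs are 0.23 × √10 = 0.73 and 0.32 × √10 = 1.01.

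| SD of ln | Source | 80% power | 90% power |
|---|---|---|---|
| 0.2 to 0.3 | Table 3 | 1.30 to 1.49 | 1.36 to 1.58 |
| 0.32 | Table 2, intervention row | 1.53 | 1.63 |
| 0.42 | 18 events, k = 0.36 | 1.74 | 1.90 |
| 0.73 | 0.23 read as a standard error | 2.61 | 3.04 |
| 1.01 | 0.32 read as a standard error | 3.81 | 4.69 |

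The 0.42 row ignores variation in clinic volume, which would raise it, and any gain from strata or baseline adjustment, which would lower it.

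**The case against.** A reader might infer that Table 2 cannot come from the randomisation described, so that either its arm labels or its SDs must be wrong. The documents do not support that.
- The strata used 2017 data, Table 2 uses an undated 10-month window that was not fully entered, and the restriction tolerances are not given. Incomplete or uneven entry could account for part of the gap, though hardly for the small SDs.
- The gap alone is possible if clinics differ widely. The 6.6 standard errors rely on the very SDs in doubt; read as standard errors, they give t = 2.08 (p about 0.05).
- SDs below Poisson noise are not anomalous alone. With 10 clinics and no between-clinic variation, values as low as 0.23 and 0.32 arise in about a third and a quarter of samples. The conflict appears once k = 0.36 is added: both SDs are then this small in about 0.1% of runs, even with equal clinic volumes.
- Rows that are really the low and high strata would give a pattern of this kind, since a median split with a gap of 0.82 predicts a within-half SD of about 0.31. But that holds for a split on the count itself. The strata were split on the 2017 percentage, for which simulation gave a mean gap of only about 0.44 and SDs of 0.43 to 0.49. Exchanging the two arm labels changes nothing, because the ratio stays 2.27.

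Two further inferences also fail. The site criterion of at least 15 smear-positive cases a year does not discredit the intervention row: it counts 2015 diagnoses, and the SAP's average clinic would itself have only 178 × 0.067 = 11.9 outcome events a year. Nor would a wrong arm code corrupt the baseline covariate of the primary model, which is each clinic's own count; the documents give no sign of miscoding.

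The best defence of Table 3 is that strata and baseline adjustment reduce the relevant SD. If the strata split the clinics perfectly on their true percentage, k would contribute 0.35 × √(1 − 2/π) = 0.21, and the total would be √(1/18.0 + 0.21²) = 0.32, just above the range used. Baseline adjustment could lower it further. But the SAP labels its SD as within-arm and gives no correlation from which to claim that gain.

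The SAP also promises a recalculation, and Annex Table 4b will show baseline counts by clinic and arm. Both help. However, the amendment log, which runs to July 2021 and corrects the 268 figure in this same section, records no recalculation.

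**Conclusion.** The point stands as a discrepancy to be resolved, not as proof of a particular error. Gap and SDs together are very unlikely under section 4.1 and k = 0.36: at most about 1 in 2,800 by enumeration (4/11,392), and never seen in simulation. Standard errors printed as SDs, rows that are not the arms, and incomplete entry contributing to the gap all remain open.

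Whatever the cause, 0.2 to 0.3 is not a supported range for the within-arm SD. It excludes one of the two SDs printed just above it, and k = 0.36 alone gives 0.35. Defensible detectable ratios at 80% power run from 1.53 (SD 0.32) through about 1.74 (SD 0.42) to about 2.6 to 3.8 if the SDs are standard errors. The word conservative is therefore not justified. These figures rest on a two-sided 5% test, 9 effective clusters per arm, a log-normal reading of k and the SAP's planning volume.

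The consequence is limited. The 20 clinics were fixed before this calculation, and neither table enters the primary model. This should be fixed, but it does not threaten the estimand or the test.

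**What to change.** The trial statistician should:
1. Recompute Table 2 from the clinic-level baseline counts, by arm and separately by stratum. State the dates of the window and how complete the data are, and print the overall SD that the text says was assessed.
2. Check the 20 arm codes against the randomisation list.
3. Correct Table 2 and the sentence on the lower intervention baseline if the check requires it.
4. Restate Table 3 with the verified SD, or with one consistent with k = 0.36, and drop the word conservative. Any gain claimed from strata or baseline adjustment should be shown with the residual SD it assumes.
5. Record the recalculation in the SAP amendment log.

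The cost is a few hours of statistician time on data already held, plus a SAP correction. The price is that the stated detectable ratio will probably look less favourable.
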